### 5.3. Study Agent

The oral FMT formulation DE capsules will be provided by OpenBiome. These oral FMT capsules are considered an IND by the FDA (IND number: *PENDING*). These are encapsulated fecal microbiota. Refer to Finch Therapeutics BBMF #17192. The fecal microbiota are human-derived microbes. The human source generating the fecal microbes has been extensively screened for infectious pathogens and microbiome mediated diseases using a standardized process (refer to OpenBiome's BBMF#15542, Section F). Additionally, the capsule delivery vehicle enables *targeted deposition* of the investigational active pharmaceutical ingredient into the colon.

#### 5.4. Summary of Clinical Data

FMT-instillation of stool from a healthy donor into the intestine of a CDI patient has been shown to be an effective approach for the treatment of recurrent CDI. A recent randomized controlled trial of FMT in patients with recurrent CDI found a 90% success rate. Its efficacy is thought to be due to restoration of gut microbial diversity and colonization resistance. In mouse models of CDI recurrence, FMT has been shown to be highly effective at reestablishing colonization resistance to *C. difficile* by restoring bacterial community structure in the gut. Current guidelines recommend that FMT be reserved for patients who have had several episodes of recurrent CDI and have exhausted other treatment options. Because of the high risk of recurrence with antibiotic use and lack of effective therapies available, novel and innovative approaches to prevent CDI recurrence in hospitalized patients receiving antibiotics would be a major advance in the field. This is a critical gap that our research group strives to fill.

Restoration of gut microbiota and prevention of antibiotic-associated diarrhea and CDI has been studied in several clinical trials using concurrent probiotics with antibiotic therapy with conflicting, although largely positive results. Given that FMT is comprised of entire bacterial communities rather than isolated taxa, FMT offers an ecological advantage. FMT, has been shown to be a highly effective and safe intervention for treatment of recurrent CDI. A recent systematic review and pooled analysis reports FMT was 83% effective in the treatment of recurrent CDI, with few reported adverse events. Although not fully elucidated, the hypothesized mechanism of FMT for CDI is that normal colonic microbiota outcompete and competitively exclude *C. difficile*.

Recently, Osman et al presented effectiveness and safety data from a 2,050 patient cohort among OpenBiome recipients. The data suggests that among the 42 suspected adverse events, 0 were definitely related to FMT material based on NIH criteria after a comprehensive investigation (Appendix 16.1).

#### 5.5. Dose Rationale, Capsule Preparation, and Administration of Study Product

Thirty (30) DE capsules will be administered to the single dose FMT group. This dosing has been used in the past to successfully clear CDI. Five DE capsules or placebo will be administered to the daily groups every day of antibiotic treatment plus seven days post antibiotics. This dose was chosen to determine if lower doses of FMT treatment are effective at CDI prevention during antibiotic treatment and if they are well tolerated by the patient. Participants will undergo capsule administration in the following manner:

1. Document review: Confirmation/review of inclusion and exclusion criteria and contraindications
2. Safety capsules: Direct observed capsule test. Participants will ingest one inert, size 00 “safety” capsule under direct supervision of the study physician/nurse. In the CRU, for the purpose of this study, the CRU nurse will be considered a study nurse.
3. Dietary instructions: Patients in the one-time administration of 30 capsules group should maintain a clear liquid diet 8 hours prior to capsule ingestion and one hour post administration. Patients receiving the daily dosing should fast (clear liquids allowed) for a minimum of 2 hours prior to administration and one hour following administration (clear liquids allowed).
4. Capsule administration:
  - a. One-time group: Patients should ingest 30 DE capsules under the direct observation of the study physician/nurse.

Daily groups: Patients should ingest 5 DE capsules under the direct observation of the study physician/nurse while admitted to the hospital. Following discharge, patients will take 5 DE capsules daily at home. Outpatients will return to the clinic for their first dose of FMT and will ingest the first dose (five capsules) under direct observation of a study nurse/physician. There is currently no published data on home administration of DE capsules; however, this method of administration is currently being used in several studies being conducted by OpenBiome with good compliance and acceptance from the patient populations.

- b. Patients should ingest the capsules within 90 minutes of extraction from the freezer. Patients receiving FMT at home will be provided a cooler and freezer packs, a method which has been used in prior studies by OpenBiome, to keep the capsules in good condition. Patients in the daily arms of the trial should ingest the capsules upon removal from the cooler or within 90 minutes. These patients will be asked to record when the capsules are consumed in a monitoring chart.
- c. All patients should remain fasting (clear liquids allowed) for 1 hour following capsule ingestion after which they can return to a normal diet.

## **5.6. Potential Risks and Benefits to Subjects**

There are risks associated with conducting this study; however, OpenBiome and its clinical affiliates possess a unique set of resources and expertise to mitigate these risks. To clarify, the risks described below are generalized to FMT therapies that are delivered endoscopically. There is no data available that is specific to FMT therapies that are delivered orally, which is the case for DE. It is expected that the risks of oral FMT therapy will be significantly reduced because many of the risks of FMT therapy delivered via endoscope are due to the procedure itself, not the drug that is delivered.

### **5.6.1. Known Potential Risks**

In the first randomized controlled trial on FMT, mild diarrhea (94%), abdominal cramping (31%) and belching (19%) were observed on the day of colonoscopic infusion; however, these symptoms resolved within 3 hours. Of note, in follow-up, three patients who were treated with donor feces (19%) had constipation. No other adverse events related to the study treatment were reported.

There is a paucity of data on long term follow-up related to FMT. Brandt et al. conducted a retrospective multi-center study (n=77) with a follow up varying between 3 to 68 months and reported 7 deaths. However, none were related to FMT. A recent systematic review on the safety of FMT suggests there are risks including: infection (fever, bacteremia), autoimmune disease (peripheral neuropathy, Sjogren's syndrome, idiopathic thrombocytopenic purpura and rheumatoid arthritis, inflammatory bowel disease flare among patients with ulcerative colitis) and other studies have suggested a link to metabolic syndrome. However, comprehensive screening of donors should decrease any potential future risk. OpenBiome donors are highly selected with only 2.8% of candidate donors qualifying to donate after screening both infectious disease and microbiome-mediated disease (Appendix 16.3).

While there is the potential for additional risks associated with FMT treatment due to the nature of capsules, OpenBiome donors are highly screened before selection to ensure safety. OpenBiome donors undergo a rigorous clinical evaluation with an internal medicine specialist as well as a wide range of screenings for infectious pathogens.

### **5.6.2. Protection Against Risks**

To minimize risks, we will monitor all patients for fever and other signs of infection. All patients will have the phone number for the medical monitor to report any side effects. Subjects will be instructed to seek medical care emergency care if severe illness develops. If it is determined that a subject has a clinical infection due to the FMT, as determined by culture and strain-typing, standard medical care will be provided to the subject.

### **5.6.3. Potential Benefits to the Subjects**

The potential benefit to the subjects is prevention of recurrent CDI. This benefit will only apply to the subjects receiving the FMT. If this study is able to demonstrate oral FMT is able to prevent recurrent CDI in patients at risk for CDI due to current antibiotic treatment, the community at large will benefit by gaining a preventative treatment for *C. difficile*. Additionally, the identification of a non-antibiotic treatment for infection prevention is a benefit to society.

Additionally, a number of case reports have reported decolonization of antibiotic resistant bacteria following FMT, including carbapenem-resistant *Enterobacteriaceae* (CRE), extended spectrum beta-lactamase (ESBL)-producing *Escherichia coli* and methicillin-resistant *Staphylococcus aureus* (MRSA) enteritis. Participants enrolled in this study who have received an FMT may benefit from close health surveillance at follow up consultations in comparison to non-participants.

#### **5.6.4. Risk Minimization**

As stated in section 5.6.2, we will ensure patients know the signs of infection and know who to contact if they develop an illness during the study period. Additionally, we will administer the capsules under direct supervision while the patient is in the hospital. Subjects' tolerance for consuming capsules will be established at enrollment visit by giving them an inert size 00 capsule.

### **6. STUDY OBJECTIVES AND PURPOSE**

The goal of this study is to assess the effect of daily oral FMT and a single dose FMT on the gut microbiota in patients currently undergoing antibiotic treatment.

- Primary Objective: To assess the efficacy of oral FMT on the composition and function of the gut microbiota compared to the placebo groups.
- Secondary Objective: To assess the safety and feasibility of both oral FMT regimens versus placebo.
- Secondary Objective: To determine the rate of CDI during oral FMT versus placebo.
- Secondary Objective: To determine the rate of *C. difficile* colonization during oral FMT compared to placebo.
- Secondary Objective: To evaluate time to CDI and/or colonization with *C. difficile*.

### **7. STUDY DESIGN AND ENDPOINTS**

#### **7.1. General Design**

This is a phase II, double-blind, randomized, placebo controlled trial assessing the effects of either daily (group 1) or one-time (group 2) oral FMT on the composition and function of the gut microbiome compared to placebo (group 3) in a population of patients with a history of CDI currently on antibiotics for a reason other than current CDI. Participants will be 18 years of age or older, have 72 hours or less of an antibiotic and meet all inclusion criteria while having no exclusion criteria prior to randomization. Patients will be randomized at a 1:1:1 ratio using permuted blocks (block size=10). Randomization will be double-blinded. Each subject (n=30) will be followed for 6 months. Stool samples will be taken at baseline and every 3 days  $\pm$  1 day from all subjects regardless of treatment group while the patient is hospitalized. If/when a patient is discharged from the hospital, the patient will continue to provide stool samples every three days during FMT. Following completion of the FMT intervention, the patient will provide stool samples once weekly for the 1 month follow-up period. All patients will be asked to complete a patient diary to report diarrhea history.

Up to one gram of stool will be sent to Finch therapeutics for additional 16s rRNA sequencing.

**Intervention:** There are 2 intervention groups for this study. Both groups will receive oral FMT capsules from OpenBiome for the prevention of CDI during antibiotic treatment. All patients will fast (clear liquids only) for a minimum of 2 hours prior to administration and 1-hour post-administration for the daily groups and be fasting for 8 hours prior and 1 hour post FMT consumption for the single dose group. The capsules will be administered in the patient's room while admitted or in the ID clinic or CRU if the patient is an outpatient and the first dose will occur under direct observation. Patients admitted to the hospital as well as all patients in the single dose group will be observed for 30 minutes post-administration to ensure the capsules are safely consumed. Hospitalized patients need to be observed 30-minutes post-administration following only the first dose. As mentioned above, the oral FMT capsules will be administered in two ways:

**Group 1:** This group will receive daily oral FMT capsules. Five capsules will be administered each day of the

patient's antibiotic treatment plus seven days post-antibiotic treatment.

**Group 2:** This group will receive 30 oral FMT capsules one time 48-72 hours following completion of antibiotic treatment.

**Oral FMT capsules:** Capsules contain fecal microbiota sourced from healthy donors and screened for pathogens.

**Control:** The control is an oral placebo capsule identical to the FMT capsules given to the intervention groups and will be provided by OpenBiome. The placebo capsule consists of glycerol and saline and will be administered daily as five capsules per day during the duration of antibiotic treatment plus an additional seven days post-antibiotic treatment (group 3). Patients will be fasting (clear liquids allowed) for at least 2 hours prior to administration and at a minimum of 1-hr post-administration (Appendix 17.1)

## 7.2. Study Outcome Measures

### 7.2.1. Primary Study Outcome Measures

The primary outcome of the study is the microbial composition and function of the gut following oral FMT treatment during concurrent antibiotic treatment. Microbial composition of the stool will be assessed using 16s rRNA targeted amplicon sequencing at baseline, every three days ( $\pm 1$  day) during hospitalization and during the intervention, and weekly for one month following completion of the FMT intervention. At the same time points, function of the gut microbiome will be assessed using shotgun metagenomics.

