## 2. STUDY SUMMARY

Title	A phase II randomized, double-blind placebo-controlled trial to determine if fecal microbiota transplantation is efficacious for hospitalized patients with C. difficile infection history during antibiotic treatment
Short Title and Precis	The GRAFT study
Protocol Number	2017-0789
ClinicalTrials.gov number	NCT03621657
Funding Sponsor	Agency for Healthcare Research and Quality (AHRQ) [name] [contact]
Study Product	OpenBiome fecal microbiota preparation capsule [FMT Capsule DE]
Phase	Phase II study
Methodology	Randomized, double-blind, placebo-controlled trial
Study Duration	1 year
Study Center(s)	Single-center, University of Wisconsin Hospitals and Clinics
Objectives	The primary objective of this study is to compare the gut microbiota and clinical outcomes of oral FMT during antibiotic treatment, immediately following antibiotic treatment, and placebo. The second objective is to assess the safety and feasibility of daily oral Fecal Microbiome Transplant (FMT) as a treatment option.
Number of Subjects	30 (1:1:1 randomization), 10 subjects per group
Diagnosis	Changes in the gut microbiota and C. difficile infection (CDI)
Main Inclusion Criteria	Receiving antibiotics for reasons other than CDI following a recent CDI episode (within last 90 days)
Main Exclusion Criteria	Bowel obstruction or gut motility issues, severely immunocompromised, or admitted to the ICU.
Study Product, Dose, Route, Regimen	FMT will be delivered through oral capsules prepared by OpenBiome. It will be administered in one of two ways depending on the arm of the trial. 1) A low dose of 5 capsules per day during antibiotic treatment and for seven days following conclusion of antibiotics. 2) A single dose of 30 capsules (22.5g) of oral FMT will be given 48-72 hours after antibiotic treatment conclusion.
FDA status of product	Encapsulated fecal microbiota preparation (FMT Capsule DE). Please refer to Finch Therapeutics BBMF # 17194.
	Sourced from human-derived microbes. Please refer to OpenBiome BBMF # 15543, Section F.
	IND: 18262

**Duration of administration** Group 1: 5 capsules of oral FMT per day undergoing antibiotic treatment and for 7 days following conclusion of antibiotic treatment.

Group 2: 30 capsules taken 48-72 hours following conclusion of antibiotic treatment

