## 10. LABS

Tests will not be done in a CLIA-certified lab. Samples will be collected from the patient and brought to the lab while the subject is admitted. After discharge, the subject will mail the samples to the laboratory for processing. Samples will be labeled with only an ID number. We will not disclose any results to the patients. Data generated by the laboratory procedures will be used to determine the patient's colonization status with MDROs and *C. difficile* at baseline and to determine if colonization status changes during the course of the trial.

Laboratory procedures include:

- Bacterial DNA isolation from stool
- 16s rRNA sequencing of the v4 region
- Culture to identify MDROs, including but not limited to: MRSA, Vancomycin-resistant enterococcus (VRE), and *C. difficile*
- Polymerase Chain Reaction (PCR)

Data from laboratory procedures will also be used to determine if the FMT treatment has an impact on the patients gut microbiome. All stool remaining following the completion of laboratory procedures will be stored at -80°C and labeled with the sample ID and held for future analysis.

Up to one gram of stool will be sent to Finch therapeutics for additional 16s rRNA sequencing.

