### *All subjects:*

All subjects will provide stool samples every three days after the baseline visit until their FMT intervention is complete and weekly for one month following conclusion of FMT treatment. Patients will also be asked to complete a patient diary daily from enrollment through the first month of follow-up. If a subject is discharged during the study period, he/she will be asked to complete the patient diary from home as well as provide stool samples to be mailed back to the lab for processing. A member of the study team will also call or email patients on a weekly basis during the intervention and follow-up period to remind to complete the stool sample

as well as record any adverse events. If a patient is discharged, vital signs, general health status, and medications at discharge will be assessed through the medical record.

At the end of the 1 month follow-up (last week of providing the weekly, post-FMT stool samples), patients will receive a call assessing the following:

- Clinical assessment by study nurse or physician, specifically evaluating adverse events related to the intervention.
- Data collection at visit:
  - Interim medical history with focus on infectious diseases
  - Concomitant medication
  - Significant changes in diet
  - Changes in stool consistency (Bristol Stool Scale) and frequency
  - General health status
  - Adverse events (NIH criteria)

A table of all study events is provided in Appendix II, 17.2 (Study Calendar).

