#### **12.3. Final Analytic Plan**

Categorical data will be described using descriptive statistics (proportions and percentages). Continuous data will be described using means and standard deviations (normally distributed data) or using medians and interquartile range (non-parametric data). Appropriate comparative statistical tests will be chosen based

in the variable types (categorical, dichotomous, continuous) and distribution (parametric, non-parametric) and will be used to describe significant differences between intervention and control groups. Where appropriate, point estimates and confidence intervals will be reported. The p-value will be two tailed with a significance level of 0.05.

The microbiome will be assessed using 16s rRNA targeted amplicon sequencing. Sequences will be cleaned and binned into operational taxonomic units and assigned taxonomy. Differences within individuals will be assessed using the Inverse Simpsons Diversity index and comparisons between study groups will be done using the Bray Curtis dissimilarity matrix and visualized using principal coordinates analysis.

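### The primary microbiome outcome does not separate stools taken while Group 1 swallows donor capsules daily from stools taken afterwards, so a diversity difference during dosing may partly or wholly be capsule contents

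*Combined protocol and SAP*

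**What the plan says.** Section 7.2.1 defines the outcome in one sentence: "The primary outcome of the study is the microbial composition and function of the gut following oral FMT treatment during concurrent antibiotic treatment". On the composition part it states: "Microbial composition of the stool will be assessed using 16s rRNA targeted amplicon sequencing at baseline". Sampling then recurs at three-day intervals "during hospitalization and during the intervention, and weekly for one month following completion of the FMT intervention". Gut function is measured on those same occasions by shotgun sequencing. Section 11.2 applies the schedule to every arm: "All subjects will provide stool samples every three days after the baseline visit until their FMT intervention is complete", with weekly stools for a month after that.

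Under Sections 2 and 7.1, Group 1 takes five FMT capsules a day through antibiotics and for seven more days. Group 3 takes glycerol-and-saline placebo on the same calendar. Group 2 receives nothing until 48-72 hours after antibiotics, and then has "A single dose of 30 capsules (22.5g) of oral FMT".

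Section 10 lists "16s rRNA sequencing of the v4 region". Section 12.3 uses the inverse Simpson index within individuals, and "comparisons between study groups will be done using the Bray Curtis dissimilarity matrix". Section 2 adds ANCOVA and linear mixed models for longitudinal data.

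No section provides for sequencing capsule lots or donor material, strain tracking, a viability step, timing of the stool relative to that day's capsules, or an analysis that splits on-dose from off-dose stools.

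**The concern.** Every Group 1 stool collected in the intervention period after the first dose is taken from a patient who is swallowing donor stool. Its DNA is a mixture of the patient's own bacteria and capsule material, live or dead, and the planned pipeline counts all of it as the patient's microbiota. The placebo holds no fecal material, so it does not control for this. Group 2 has had no donor material in that window. The effect is therefore confined to one arm, and randomization does not remove it.

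The hypothesis in Section 5.2 is that FMT keeps diversity and function up under antibiotics, and Section 12.3 plans two-sided tests at 0.05. Capsule DNA in transit pushes Group 1 towards that result even if nothing establishes itself. The push is larger when antibiotics have depleted the patient's own bacteria, which is a plausible state in this trial. The study calendar (Section 17.2) adds a trap: for the daily groups, the column for seven days after antibiotics marks both a stool and capsule administration. A natural end-of-treatment reading would thus be on-dose.

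**Working it through.** The plan states no effect size, standard deviation or power (Section 12.1), so there is no design figure to reproduce. Three checks apply.

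**1. Share of Group 1's samples that are on-dose.** Dosing days = antibiotic days on study + 7. On-dose stools are about dosing days / 3, rounded down. Off-dose stools are the 4 weekly ones.

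| Antibiotic days on study | Dosing days | On-dose stools | On-dose share |
|---|---|---|---|
| 3 | 10 | 3 | 3/7 = 43% |
| 7 | 14 | 4 | 4/8 = 50% |
| 14 | 21 | 7 | 7/11 = 64% |

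The count stops at 14 days. For longer courses, the group labels in Section 8.4.2.2 conflict with those in Section 7.1, and the two must be reconciled.

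**2. What transit alone could do, with zero engraftment.** From Section 2, 22.5 g / 30 = 0.75 g per capsule, so 5 x 0.75 = 3.75 g a day in Group 1. Everything else is assumed, because the documents do not give it:
- stool mass M = 100-200 g a day;
- native bacteria depleted k-fold, with k = 1, 10 or 100;
- capsule material as dense in bacteria as undepleted stool;
- native inverse Simpson 3, donor 15;
- no shared taxa.

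Donor share of DNA: s = 3.75 / (3.75 + M/k). Mixed index: 1 / [(1-s)^2/3 + s^2/15]. With no shared taxa, the Bray-Curtis distance from the patient's own untreated community equals s.

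| Depletion | s (M = 200 to 100) | Inverse Simpson, from 3 |
|---|---|---|
| none | 0.018-0.036 | 3.1-3.2 |
| 10-fold | 0.158-0.273 | 4.2-5.5 (+40% to +84%) |
| 100-fold | 0.652-0.789 | 14.6-17.8 |

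As an example, at k = 10 and M = 100, s = 3.75/13.75 = 0.273 and the index is 1/(0.1763 + 0.0050) = 5.52.

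Section 9.1 lists theobroma oil and glycerol in the capsule, so equal density may be generous. At half the donor DNA density and k = 10, s = 1.875/(1.875 + M/10) = 0.086-0.158, and the index is 3.6-4.2 (about +19% to +40%).

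**3. When the weekly stools fall.** The documents say only that they are weekly. Assume that each patient's first weekly stool comes about 7 days after the last capsule.
- Groups 1 and 3: 7 + 7 = about day 14 after antibiotics. The two arms are matched in time.
- Group 2: 2 to 3 + 7 = about day 9-10. This is 4-5 days earlier.

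**The case against.** The strongest reply is that engraftment is not a stated objective. Sections 5.2 and 7.2.1 name the period of antibiotic treatment, and Section 5.4 gives competitive exclusion of *C. difficile* as the hypothesized mechanism. Donor bacteria present during antibiotics may be the intended effect. That stands as a reason to keep these stools in the analysis. It does not make passing capsule DNA evidence that the patient's own community was maintained. If transient presence is the target, the plan should say so.

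A reader might infer that the whole primary comparison should move to the weekly stools. The documents do not support that without cost. It would leave the on-antibiotic period that the hypothesis names. It would set Group 2 against placebo at different times since antibiotics. It would also lose patients who develop CDI, because Sections 11.3 and 11.4 end their participation with at most a final stool. That sits badly with the intention-to-treat statement in Section 9.8.

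A reader might also infer that sequencing can never tell donor from patient. Shotgun data could separate the strains if the capsule lots were sequenced, which is not planned. What even that could not do is distinguish transit from engraftment while dosing continues.

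Finally, the plan assigns no weights to on-dose and off-dose stools, and a rise that disappears after dosing would be visible in the scheduled data. That is true, but nothing in the plan requires anyone to look for it before drawing the conclusion.

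**Conclusion.** The point holds as a limit on interpretation that the plan should state and analyse. During dosing, a Group 1 versus placebo difference in inverse Simpson or Bray-Curtis may partly or wholly be capsule contents, and the plan as written neither labels nor separates those stools. They make up about 43-64% of Group 1's post-baseline samples for 3-14 antibiotic days.

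The size is not established. Only the 3.75 g a day comes from the documents. The result runs from negligible without depletion to dominant at 100-fold, and no document reports the degree of depletion. No taxa in common between two human gut communities is an extreme assumption. A reader might infer that daily FMT will look effective whatever it does; the calculation shows only that it can. Nor does a Bray-Curtis difference show higher diversity: it says that communities differ, and inverse Simpson carries the diversity claim.

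**What to change.** In Sections 7.2.1 and 12.3:

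- Keep the on-antibiotic stools, but analyse and report on-dose and off-dose stools separately, for example with a dosing-period term and its interaction with arm in the mixed model.
- Label Group 1's on-dose stools as including capsule material, and draw no conclusion from them alone that diversity or function was maintained.
- Base that conclusion on a pre-specified Group 1 versus Group 3 comparison of the weekly post-dosing stools, which share a dosing calendar.
- Align comparisons with Group 2 by days since antibiotics ended, or adjust for it.
- Include the early-termination stool of patients who stop for CDI, or handle its absence in a sensitivity analysis. In Group 1 that stool may itself follow a capsule closely and should be labelled accordingly.

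This needs no new visit, sample or participant, and should be settled before data are seen. Sequencing the capsule lots would help to identify donor strains, but is extra laboratory work and not essential to the change. The cost is in what may be claimed. Group 1's on-antibiotic result carries less weight, and the off-dose comparison measures persistence from about two weeks after antibiotics, assuming the 7-day gap used above.
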